7. PLANNED ANALYSIS

The placebo group will consist of all placebo treated subjects, regardless of the dose group in which they were treated.

Safety analysis (refer to [Section 7.8](#)) will be performed by _____ and will be presented in Sections 15.1 to 15.4 of the CTR and in Appendix 16.2 and 16.1.13.1.

Inferential statistical analyses of PK endpoints (refer to [Section 7.5.2](#)) will also be performed by _____ and will be presented in Section 15.5 of the CTR and in Appendix 16.1.13.3.

Descriptive data analysis of PK parameters and concentrations will be performed by _____ department Translational Medicine and Clin. Pharmacology (TMCP) and will be presented in Section 15.6 of the CTR.

Descriptive and inferential statistical analyses of PD endpoints (refer to [Sections 7.6](#)) will be performed by _____ and will be presented in Section 15.7 of the CTR and in Appendix 16.1.13.6.

The format of the listings and tables will follow the standards defined in the BI corporate guideline “Reporting of Clinical Trials and Project Summaries” [001-MCG-159] ([6](#)) with the exception of those generated for PK-calculations.

The individual values of all subjects will be listed, sorted by treatment group, subject number, and visit.

The listings will be included in Appendix 16.2 of the CTR.

For end-of-text tables, the set of summary statistics for non-PK parameters is:

N	number non-missing observations
Mean	arithmetic mean
SD	standard deviation
Min	minimum
Median	median
Max	maximum

For analyte concentrations, the following descriptive statistics will additionally be calculated:

CV	arithmetic coefficient of variation
gMean	geometric mean
gCV	geometric coefficient of variation

For PK parameters, the following descriptive statistics will additionally be calculated:

CV	arithmetic coefficient of variation
gMean	geometric mean
gCV	geometric coefficient of variation
P10	10th percentile
Q1	1st quartile
Q3	3rd quartile
P90	90th percentile

The data format for descriptive statistics of concentrations will be identical with the data format of the respective concentrations. The descriptive statistics of PK parameters will be calculated using the individual values with the number of decimal places as provided by the evaluation program. Then the individual values as well as the descriptive statistics will be reported with three significant digits in the CTR.

Tabulations of frequencies for categorical data will include all possible categories and will display the number of observations in a category, as well as the percentage (%) for each treatment group. Percentages will be rounded to one decimal place and will be based on all subjects in the respective subject set whether they have non-missing values or not. The category 'missing' will be displayed only if there are actually missing values.

Units of variables should be given in the titles or column/row descriptors in square brackets (e.g. [mg]).

Exclusion of PK parameters

The ADS ADPP (PK parameters) contains column variables APEXC and APEXCO indicating inclusion/exclusion (APEXC) of a PK parameter and an analysis flag comment (APEXCO). All analyses based on the PKS will include parameters if they are not flagged for exclusion, that is APEXC is equal to “Included”.

Exclusion of PK concentrations

The ADS ADPC (PK concentrations per time-point or per time-interval) contains column variables ACEXC or ACEXCO indicating inclusion/exclusion (ACEXC) of a concentration and an analysis flag comment (ACEXCO). Exclusion of a concentration depends on the analysis flag comment ACEXCO. For example, if ACEXCO is set to ‘ALL CALC’, the value will be excluded for all types of analyses based on concentrations. If ACEXCO is set to ‘DESC STATS’, the value will be excluded from descriptive evaluations per planned time point/time interval. If ACEXCO contains the addition ‘TIME VIOLATION’ or ‘TIME DEVIATION’, the value can be used for further analyses based on actual times. If ACEXCO is set to ‘HALF LIFE’, the value will be excluded from half-life calculation (and, as a consequence, any calculation that relies on λ_z) only; the value is included for all other analyses.

Further details are given in 001-MCS-36-472_RD-01 “Noncompartmental Pharmacokinetic / Pharmacodynamic Analyses of Clinical Studies” (5) and 001-MCS-36-472_RD-03 “Description of Analytical Transfer Files and PK/PD Data Files” (7).

7.1 DEMOGRAPHIC AND OTHER BASELINE CHARACTERISTICS

Only descriptive statistics are planned for this section of the report, based on the TS.

The data will be summarised by treatment group and in total.

7.2 CONCOMITANT DISEASES AND MEDICATION

Frequency tables are planned for this section of the report, based on the TS.

Concomitant diseases will be coded using the latest version of the coding system of the Medical Dictionary for Drug Regulatory Activities (MedDRA). Medications will be coded using the latest version of the World Health Organization Drug Dictionary (WHO-DD). The coding version number will be displayed as a footnote in the respective output.

The diagnoses and medications will be listed. Subjects without any concomitant diagnoses or concomitant therapies should be marked with a “No” in the respective column.

The relevance of the concomitant therapies to the evaluation of PK will be decided no later than at the RPM/DBLM.

7.3 TREATMENT COMPLIANCE

Section 4.3 of the CTP: *Compliance will be assured by administration of all trial medication in the study centre under supervision of the investigating physician or a designee. The measured plasma concentrations and/or urinary excretion will provide additional confirmation of compliance.*

It is not intended to list the compliance separately. Any deviations from complete intake will be addressed in the RPM/DBLM and described in the CTR.

7.4 PRIMARY ENDPOINT

Refer to TSAP [Section 7.8](#) for a description of the analysis of safety and tolerability of BI 730460.

7.5 SECONDARY ENDPOINTS

7.5.1 Key secondary endpoints

This section is not applicable as no key secondary endpoints have been specified in the protocol.

7.5.2 Secondary endpoints

Assessment of dose proportionality – SRD part

Dose proportionality of the secondary PK endpoints $AUC_{0-\infty}$ and C_{max} in plasma of BI 730460 will be explored using the power model that describes the functional relationship between dose and PK endpoints based on the PKS. The basic model consists of a regression model applied to log-transformed data (log-transformation refers to using the natural logarithm). The corresponding ANCOVA (Analysis of Covariance) model includes the logarithm of the dose as a covariate.

The model is described by the following equation:

$$Y_{ij} = \alpha + \beta * X_i + \epsilon_{ij}$$

where

Y_{ij} logarithm of the PK endpoint for subject j at dose level i ;
where $i = 1, 2, \dots, 6, j = 1, 2, \dots, 6$,

α intercept parameter;

β slope parameter;

X_i logarithm of dose i ;

ϵ_{ij} random error associated with subject j at dose level i (assumed to be independent and identically normally distributed).

Section 7.1.3 of the CTP: *This equation can be fit as a linear regression model. Based on the estimate for slope parameter (β), a 2-sided 90% CI for the slope will be computed. Perfect dose proportionality would correspond to a slope of 1. The assumption of a linear relationship between the log-transformed pharmacokinetic endpoint and the log-transformed dose will be checked.*

According to the Reference Document 3 of the Boehringer Ingelheim (BI) Statistical Position Paper on Statistical Methods for PK ([14](#)), the 90% confidence intervals (CI) should be considered for the assessment of dose proportionality. Therefore, the 90% CI will be used instead of the 95% CI.

This analysis will be accomplished by using the XPKISTAT macro (design DB), based on the PKS.

If dose proportionality over the entire dose range investigated cannot be shown, an attempt will be made to identify dose range(s), where dose proportionality can be assumed.

Graphical displays:

To support the analyses of dose proportionality, a regression plot will be performed, where the logarithm of dose is depicted versus logarithm of PK endpoint, including the estimated regression line from the power model and reference line of perfect proportionality ($\beta=1$).

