#### 1.2.5 Clinical experience in humans

This is the first-in-man study. Clinical data are not available up to date for BI 730460.

To date preliminary results are available at BI from a similar small molecule

This study was completed on 15 August 2017 and consisted of 2 parts. The SRD part was a partially randomised, single-blind, placebo-controlled trial to investigate safety, tolerability, pharmacokinetics and pharmacodynamics of single rising doses of administered as oral solution (2 mg and 8 mg) and film-coated tablets (doses of 25 mg, 50 mg, 100 mg, 200 mg, 400 mg and 800 mg) to 72 healthy male volunteers. The BA part was a randomised, open label, single-dose, three-way crossover bioavailability comparison of 25 mg in 12 healthy male volunteers to explore the relative bioavailability of tablet fasted versus oral solution fasted and the influence of food on the bioavailability of tablet fasted versus tablet fed.

Safety evaluations included physical examination, vital signs, ECG, laboratory tests, and adverse events (AEs) and demonstrated that was safe and well tolerated up to the 800 mg dose. AEs, which generally reflected commonly-occurring events of short duration, and were mostly mild or moderate in severity, were distributed without discernable trend among recipients of placebo and rising dose levels of . No serious AEs were reported.

Following administration of the tablet, [redacted] was absorbed with a  $T_{max}$  between about 2 to 3 hours. Thereafter, plasma concentrations decreased rapidly in a mono- or biphasic manner with an estimated terminal half-life ( $t_{1/2}$ ) ranging from approximately 20 to 27 hours. The preliminary PK data suggest that the exposure ( $AUC_{0-24}$ ) to [redacted] increased in a dose-proportional manner for the oral solution between 2 and 8 mg and for the tablet up to 50 mg, and thereafter increased in a less-than-dose-proportional manner, with approximately 1.5-fold increase in exposure with each 2-fold increase in dose up to 800 mg. Comparing the exposures of tablets in the fasted state, it can be noted that an 8-fold increase in dose from 25 to 200 mg and a 16-fold increase from 25 to 400 mg only led to AUC increases of 4.4-fold and 6.6-fold, respectively. After single dosing, the steady-state trough level ( $C_{24}$ ) of 140 nM for the efficacy of [redacted] was only exceeded in dose groups  $\geq 100$  mg instead of at 25 mg as originally predicted.

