#### 7.1.3 Model

##### SRD part:

The basic model for the investigation of dose proportionality will be a power model that describes the functional relationship between the dose and PK endpoints.

$$\exp(Y_{ij}) = \alpha' * \exp(X_i)^\beta * \varepsilon'_{ij}$$

The model consists of a regression model applied to log-transformed data. The corresponding ANCOVA model includes the logarithm of the dose as a covariate.

Together with  $\alpha' = \exp(\alpha)$  and  $\varepsilon'_{ij} = \exp(\varepsilon_{ij})$ , taking natural logarithms converts this model to a linear form as follows:

$$Y_{ij} = \alpha + \beta * X_i + \varepsilon_{ij}$$

where

$Y_{ij}$	logarithm of the pharmacokinetic endpoint for subject $j$ at dose level $i$ ; where $i = 1, 2, \dots, 9, j = 1, 2, \dots, 6$ ;
$\alpha$	intercept parameter;
$\beta$	slope parameter;
$X_i$	logarithm of dose $i$ ;
$\varepsilon_{ij}$	random error associated with subject $j$ at dose level $i$ (assumed to be independent and identically normally distributed).

This equation can be fit as a linear regression model. Based on the estimate for slope parameter ( $\beta$ ), a 2-sided 95% CI for the slope will be computed. Perfect dose proportionality would correspond to a slope of 1. The assumption of a linear relationship between the log-transformed pharmacokinetic endpoint and the log-transformed dose will be checked.

If dose proportionality over the entire dose range investigated cannot be shown, an attempt will be made to identify dose range(s), where dose proportionality can be assumed.

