## 7.2 NULL AND ALTERNATIVE HYPOTHESES

Safety and tolerability of different dose groups of BI 730460 are to be determined on the basis of the investigated parameters in comparison to placebo. It is not planned to test any statistical hypotheses with regard to these variables in a confirmatory sense. Instead, they will be described in their entirety and evaluated by descriptive statistical methods.

In the SRD part, for the evaluation of dose proportionality, a two-sided 95% confidence interval (CI) of the slope will be computed. However, the CI will have to be interpreted in the perspective of the exploratory character of the study, i.e. as interval estimate for effects in the present data.

The relative bioavailability of BI 730460 will be estimated by the ratios of the geometric means (test/reference) for the secondary PK endpoints. Additionally, their two-sided 90% CIs will be provided. This method corresponds to the two one-sided t-tests procedure, each at the 5% significance level. Since the main focus is on estimation and not on testing, an acceptance range was not specified, that is, no hypothesis will be tested.

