#### SRD Part: Assessment of dose proportionality

Dose proportionality of the secondary pharmacokinetic endpoints will be explored based on the regression model described in Section 7.1.3. Based on the estimate for slope parameter ( $\beta$ ), a 2-sided 95% CI for the slope will be computed. Perfect dose proportionality would correspond to a slope of 1. The assumption of a linear relationship between the log-transformed pharmacokinetic endpoint and the log-transformed dose will be checked.

If dose proportionality over the entire dose range investigated cannot be shown, an attempt will be made to identify dose ranges, where dose proportionality can be assumed.

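### Does the SAP need a written rule for when dose proportionality counts as shown, and over which doses?

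*SAP*

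**What the plan says.** SAP 7.5.2 fits the power model, an ordinary regression of the log PK endpoint on log dose, to AUC0-∞ and Cmax for the six dose groups that were given. It names slope 1 as perfect proportionality, asks for a linearity check, and adds a plot with the fitted line and a slope-1 reference line.

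The fallback has a trigger, "If dose proportionality over the entire dose range investigated cannot be shown", and an outcome, "an attempt will be made to identify dose range(s), where dose proportionality can be assumed". Protocol 7.3.2 has nearly the same outcome ("an attempt will be made to identify dose ranges, where dose proportionality can be assumed"), as does protocol 7.1.3. None of these sections attaches an acceptance range, a test, a list of candidate ranges or a minimum number of doses.

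Protocol 7.2 says how the slope interval is to be read: in light of the study's exploratory character, "as interval estimate for effects in the present data".

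On the level of the interval, SAP 7.5.2 prints "a 2-sided 90% CI for the slope will be computed" under a label that attributes it to protocol 7.1.3. The protocol sentence reads "a 2-sided 95% CI for the slope will be computed". SAP section 4 and the next paragraph of SAP 7.5.2 both state that 90% replaces 95%.

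**The concern.** The trigger and the outcome are both worded as verdicts, while the only numeric reference is slope 1. A reader could take an interval containing 1 as enough. That reading rewards imprecision: the shorter the range, the wider the interval, and the more easily it contains 1. Two analysts could then report different proportional ranges from the same data.

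Dose proportionality is part of the secondary objective (protocol 2.2), and the fallback may well be used. Protocol 1.2.5 describes a similar compound whose tablet exposure was proportional up to 50 mg and then showed an "approximately 1.5-fold increase in exposure with each 2-fold increase in dose up to 800 mg". It adds that 8-fold and 16-fold dose increases from 25 mg "only led to AUC increases of 4.4-fold and 6.6-fold, respectively".

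The 90%/95% mismatch looks like a second fault, because text attributed to the protocol is not what the protocol says.

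**Working it through.** The documents give no power, error rate or precision for this analysis, and protocol 7.6 says the SRD sample size has no power basis. So there is no figure to reproduce. The check asks how an interval-contains-1 rule would behave if someone applied it.

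**Inputs**
- Doses 2, 8, 25, 50, 100 and 200 mg, with 6 active subjects each (SAP 6.1).
- Two-sided 90% interval (SAP 7.5.2).
- Between-subject gCV is not given for these endpoints. 20%, 30% and 50% are assumptions.
- Illustrative slopes from protocol 1.2.5: ln 1.5 / ln 2 = 0.585; ln 4.4 / ln 8 = 0.71; ln 6.6 / ln 16 = 0.68. They belong to a different compound, and the text reports its exposure as AUC0-24.

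**Width of the interval**

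σ = √ln(1 + gCV²), which is 0.198, 0.294 and 0.472 for the three gCVs. Half-width = t(0.95, 6k − 2) × σ / √Sxx for k doses. For 50-200 mg the log doses lie ln 2 apart, so Sxx = 12 × (ln 2)² = 5.77 and √Sxx = 2.401. At gCV 30%:

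| Range (mg) | t | √Sxx | Half-width |
|---|---|---|---|
| 2-200 | 1.691 | 9.283 | 0.053 |
| 2-50 | 1.717 | 5.975 | 0.084 |
| 50-200 | 1.746 | 2.401 | 0.213 |
| 100-200 | 1.812 | 1.201 | 0.443 |

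**Chance that one given range contains 1 when the true slope is 0.585** (noncentral t; gCV 20/30/50%)
- 2-200 mg: about 0% at each gCV.
- 50-200 mg (three doses): 0.1 / 5.5 / 35%.
- 100-200 mg (two doses): 24 / 53 / 74%.

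**Chance that at least one shorter contiguous range contains 1, given that the full range does not** (simulation, constant slope)

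| True slope | At least 3 doses, gCV 20/30/50% | At least 2 doses, gCV 20/30/50% |
|---|---|---|
| 0.585 | 0.2 / 11 / 66% | 62 / 97 / 100% |
| 0.7 | 6 / 46 / 93% | 94 / 99.9 / 100% |

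A constant slope over 2-200 mg is not the pattern in protocol 1.2.5, so a bent pattern was also run: slope 1 up to 50 mg and 0.585 above. Given that the full-range interval excludes 1, the interval for 2-100 mg contains 1 in about 46 / 64 / 70% of trials. At gCV 50% the full-range interval itself contains 1 in about 37% of trials, so on this rule the fallback would not start in those.

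**What the plan asks for instead**

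No section makes an interval containing 1 sufficient. Protocol 7.2 reads it as an estimate. The slope is reported with its interval, so the width is visible: at gCV 30%, an estimate of 0.80 for 50-200 mg would appear as 0.80 ± 0.213, or 0.59 to 1.01. SAP section 7 adds geometric means and gCVs for PK parameters, and 7.5.2 adds the linearity check and the plot. A reader can check any proposed range against these.

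**The 90%/95% sentence**

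Protocol 7.1.3 says 95%, the sentence in SAP 7.5.2 attributed to it says 90%, and SAP section 4 says 90% will be used instead of 95%. Only the attribution is wrong. The level to be computed is clear.

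**The case for a change.** The best case for a change is that the gap is real, the objective is a secondary one, and the repair is cheap. One could tabulate the slope and 90% interval for the full range and the nine shorter contiguous ranges of at least three doses (2 + 3 + 4 = 9), and state that containing 1 is not enough. The documents do not fill the gap elsewhere: the position paper is cited only for the 90% level, and the macro named in SAP 7.5.2 is not described, so neither can be assumed to hold a rule.

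What stands is that the rule is unwritten and that an interval-contains-1 rule would be a poor one, above all for two-dose ranges or high variability.

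What does not follow is that the table would cure this. A sentence saying what is not enough still leaves open what is enough, so two analysts could still differ.

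Adding the dose-normalised ratio r^(β − 1), with r the highest dose over the lowest, brings its own difficulty, because it assumes a straight line on the log scale. In the bent pattern the expected fitted slope over 2-100 mg is 0.949, giving 50^(0.949 − 1) = 0.82, while the true ratio is 2^(0.585 − 1) = 0.75.

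**Conclusion.** No change is needed. The missing rule is a gap in detail in an analysis that the plan calls exploratory, with no hypothesis test and no acceptance range. No dosing decision waits on it: escalation relied on a separate preliminary PK analysis (protocol 7.3.4) and had already stopped (SAP section 4). An analyst can fill the gap sensibly by reporting the slope and interval for each range examined, beside the linearity check and plot.

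The mislabelling rates describe a rule that the plan does not state, and they vary widely. With at least three doses and slope 0.585 they run from 0.2% to 66% as the assumed gCV goes from 20% to 50%. They also rest on slopes borrowed from another compound. They show why an interval containing 1 should not be read as proof of proportionality, but not that following the plan as written gives a wrong result.

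The 90% printed under the protocol's section number is a clerical slip with no effect on the analysis, since the change is declared twice.

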7.7 EXTENT OF EXPOSURE

Descriptive statistics are planned for this section of the report based on the TS. The date and time of drug administration will be listed for each subject.

7.8 SAFETY ANALYSIS

All safety analyses will be performed on the TS.

If not stated otherwise, the safety results will be sorted by treatment group.

The safety data for treated subjects who failed to complete the study (dropouts or withdrawals) will be reported as far as their data are available. All withdrawals will be documented and the reason for withdrawal recorded.

7.8.1 Adverse events

AEs will be coded with the most recent version of MedDRA.

The analyses of AEs will be descriptive in nature and will be based on BI standards as presented in the corporate guideline: “Analysis and Presentation of Adverse Event Data from Clinical Trials” [001-MCG-156] ([9](#)).

The standard AE analyses will be based on the number of subjects with AEs (and not on the number of AEs).

For analysis, multiple AE occurrence data on the electronic case report form (eCRF) will be collapsed into an AE provided that all of the following applies:

- All AE attributes are identical (lower level term (LLT), intensity, action taken, therapy required, seriousness, reason for seriousness, relationship, outcome, AE of special interest (AESI))
- The occurrences were time-overlapping or time-adjacent (time-adjacency of two occurrences is given if the second occurrence started within one hour after end of the first occurrence)

For further details on summarization of AE data, please refer to [001-MCG-156] (9).

Section 5.2.2.1 of the CTP: *The following are considered as AESIs:*

- Hepatic injury
A hepatic injury is defined by the following alterations of hepatic laboratory parameters:
 - *An elevation of AST (aspartate aminotransferase) and/or ALT (alanine aminotransferase) ≥ 3 -fold ULN combined with an elevation of total bilirubin ≥ 2 -fold ULN measured in the same blood sample, and/or*
 - *Aminotransferase (ALT and/or AST) elevations ≥ 10 -fold ULN*

These lab findings constitute a hepatic injury alert and the subjects showing these lab abnormalities need to be followed up according to the 'DILI checklist' provided in the ISF. In case of clinical symptoms of hepatic injury (icterus, unexplained encephalopathy, unexplained coagulopathy, right upper quadrant abdominal pain, etc.) without lab results (ALT, AST, total bilirubin) available, the Investigator should make sure that these parameters are analysed, if necessary in an unscheduled blood test. Should the results meet the criteria of hepatic injury alert, the procedures described in the DILI checklist should be followed.

The analysis of adverse events will be based on the concept of treatment emergent AEs.

Section 5.2.2.2 of the CTP: *The REP for BI 730460, the time interval when measurable drug levels or PD effects are still likely to be present after last administration, is not known for this first-in-human trial at this early stage of development. Therefore, all AEs reported until the end of trial examination (last per protocol contact) will be considered on treatment [...].*

For more details see the TSAP ADS plan.

According to ICH E3 (10), AEs classified as 'other significant' needs to be reported and will include those non-serious and non-significant adverse events with (i) 'action taken = discontinuation' or 'action taken = reduced', or (ii) marked haematological and other lab abnormalities or lead to significant concomitant therapy as identified by the Clinical Monitor/Investigator at the RPM at the latest.

An overall summary of AEs (including AESIs) will be presented.

The frequency of subjects with AEs will be summarized by treatment, primary system organ class (SOC) and preferred term (PT), as well as by treatment, worst intensity, primary SOC and PT. Separate tables will be provided for subjects with other significant AEs according to ICH E3 (10), for subjects with serious AEs, for subjects with drug-related AEs, for subjects with drug related serious adverse events and for subjects with AESIs.

The SOC and PTs will be sorted by frequency (within SOC). The MedDRA version number will be displayed as a footnote in the respective output.

In addition, frequencies of subjects with non-serious AEs that had an incidence of > 5% for at least one treatment will be summarised by treatment, primary SOC and PT.

For disclosure of adverse events on EudraCT additional information not included in a standard AE analysis will be performed. The following three entries will be created:

- Adverse Events per arm for disclosure on EudraCT
- Non-serious Adverse Events for disclosure on EudraCT
- Serious Adverse Events for disclosure on EudraCT

